### 9.5.2 Secondary Outcomes

#### Main Secondary Clinical Outcomes:

1. Patient Report Outcomes Measurement Information System – Anxiety Short Form 8a (PROMIS-ASF)
2. Patient Report Outcomes Measurement Information System – Pain Interference Scale (PROMIS-PISF)
3. Positive oral fluid toxicology tests for Cocaine during the final 12 weeks (weeks 13-24) of the study.
4. Positive oral fluid toxicology tests for Benzodiazepines during the final 12 weeks (weeks 13-24) of the study.

#### Exploratory Self-regulation mechanistic outcomes

1. Brief Experiential Avoidance Questionnaire (BEAQ) (EMO)
2. Difficulties in Emotion Regulation Scale (DERS-16) (EMO)
3. Perceived Stress Scale (PSS) (EMO)
4. Self-Compassion Scale (SCS) (SRP)
5. Multidimensional Assessment of Interoceptive Awareness subscales 1, 4-8 (MAIA) (SRP)
6. Nonattachment to Self Scale (NTS) (SRP)
7. Self-Critical Rumination Scale (SCRS) (SRP)
8. Experiences Questionnaire- Decentering Subscale (COG/EMO)

#### Exploratory Other Mechanistic outcomes:

1. Five Facet Mindfulness Questionnaire (FFMQ)
2. Interpersonal Mindfulness Scale (IMS)
3. Group Cohesion Questionnaire (GCQ)
4. M-ROCC Qualitative Interviews
5. Credibility/Expectancy Survey (OUD)
6. Credibility/Expectancy Survey (Stress)

#### Exploratory Clinical Outcomes:

1. Intervention retention at 24 weeks, defined as any **active BUP prescription** within the last 28 days (i.e., between Weeks 20-24 of participant enrollment).
2. Time to intervention discontinuation

3. Weekly Survey reports of BUP non-adherence [a] and diversion [b]
4. Medication-assisted treatment status at 24 weeks (including methadone, buprenorphine or naltrexone).
5. Self-reported average daily dose of BZDs prescribed over final 12 weeks
6. Beck Anxiety Inventory (BAI)
7. Pain Catastrophizing Scale (PCS)
8. Substance Craving Scale (SUBCS)
9. CAT-DI
10. CAT-ANX
11. CAT-PSY
12. CAT-MANIA
13. CAT-SUD
14. CAT- PTSD
15. CAT-SDOH

## 9.6 Data Analyses

### **Primary Outcome:**

The **main primary outcome** is biochemically-confirmed illicit opioid abstinent periods (defined by a negative oral fluid test [negative for opiate, oxycodone, fentanyl, methadone] AND no self-reported illicit opioid use), during the final 12 weeks of the study (with 6 being the highest possible number of oral fluid tests during that time period).

Negative toxicology screens have been previously used to assess effectiveness of OUD treatment. We will use an intent-to-treat design to evaluate the extent to which M-ROCC impacts biochemically confirmed illicit opioid abstinence over 6 biweekly time periods during the final 12 weeks of the study, **using Generalized Estimating Equations (GEE)**, which accounts for the clustering of individual observations over time, with covariates. This analytic approach provides reliable estimates even when data are unbalanced. GEE is also robust against misspecifications of the working correlation matrix when specifying the correct dependent-variable distribution and canonical link function. The benefit of selecting the best correlation structure is the gains in efficiency. The Quasi-likelihood Under Independence Model Criterion (QIC) will be used to ensure the best fitting working correlation structure. **For dichotomous outcomes**, we will specify a binomial distribution and a logit link function, and robust standard errors clustered at the individual-level. For **missing data**, we will implement multiple imputation methods in Stata (mi procedure). This technique creates multiple complete datasets, imputes missing values using a probabilistic simulation method (e.g., chained equations),

analyzes each dataset, and uses standard rules to combine estimates and adjust standard errors for the uncertainty of imputation.

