**Figure 1. Five affiliated primary care sites and non-affiliated recruitment sources in the MINDFUL-OBOT study**

**Figure 2. Study Schema**

## 4. SELECTION AND ENROLLMENT OF PARTICIPANTS

### 4.1 Inclusion Criteria

All of the following are required criterion for inclusion in the study:

1. 18-70 years old
2. Participant lives in Massachusetts, Connecticut, Florida, Maine, New Hampshire, New York, Rhode Island, Texas, Vermont, California, North Carolina, Virginia, Alabama, Arizona, Illinois, or Michigan.
3. Participant is currently prescribed Buprenorphine.
4. Diagnosis of opioid use disorder prescribed a stable dose of buprenorphine (at least 4 weeks)
5. Less than 90 days of abstinence (from non-prescribed opioids or benzodiazepines, cocaine, or alcohol) **OR** OUD with a co-morbid anxiety or stress disorder (as evaluated by Computerized Adaptive Testing for Mental Health [CAT-MH] or PROMIS-ASF  $\geq 55$ ).
6. Able to use an electronic device with a videocamera to attend study groups and complete questionnaires.
7. Sufficient English fluency to understand procedures and questionnaires
8. Ability to provide informed consent.

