## **Screening Assessments (Consent and Screening Visit)**

After participant consent has been obtained, the research coordinator will provide the participant with a secure REDCap link to the PROMIS-ASF, and PhenX toolkit surveys, as well as a secure link to a screening CAT-MH survey, to evaluate for eligibility prior to proceeding with baseline assessments. The RC will also supervise an oral fluid test with the participant to assess for substance use. If the screening process suggests that the participant meets exclusion criteria or brings up other questions about eligibility, then the RC will contact the PI or clinical director to review the information and decide prior to proceeding to baseline assessments. If a participant's PROMIS-ASF T score is greater than 55 (Raw > 16), then the participant will be determined to have an anxiety disorder even if it was not previously diagnosed clinically.

Since participants with opioid use disorder often have transient mental health symptoms or intoxication related to recent substance use, participants with transient symptoms related to recent substance use may be able to wait for a re-review of eligibility after 30 days.

During this screening visit, all eligible participants will be asked to fill out a Scheduling Acceptability form to rate the level of acceptability of the available study group day and time for both M-ROCC and control group times at the site, asking on a 0-10 scale how much they will be able to attend the group times.

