Based on R21 urine toxicology data, we will focus our primary outcome analysis on the impact of M-ROCC on opioid use starting 12 weeks after intervention assignment. We estimate a mean of 4.67 negative tests for all illicit opioids (opiates, oxycodone, fentanyl, methadone) out of 6 random oral fluid toxicology tests conducted during the last 12 weeks in M-ROCC (SD 1.23) ( $n=78$ ) and 4.11 negative tests for all illicit opioids in the control check-in group (SD 1.27) ( $n=78$ ). We anticipate an effect size of Cohen's  $d = 0.45$  for between-group difference in percentage of monthly positive toxicology screens. Participation of  $N=192$  individuals randomized (with an effective sample size of 156 with 78 individuals in the M-ROCC arm and 78 individuals in the control group) allows for  $> 80\%$  power to detect an effect size of 0.45 for negative toxicology for all illicit opioids between M-ROCC and control arms. This power calculation was generated assuming a t-test of the difference between two means, a 1:1 intervention to control recruitment ratio, a type I error of 0.05, a two-sided comparison, and a design effect of 1.23 derived from an ICC of 0.01 with 8 group clusters with average cluster size of 24, which represents the average number of people randomized in each monthly cohort to either live-online M-ROCC or the live-online control group. This level of cluster was selected because it will encompass cohort effects. As the primary outcome will be analyzed in an intent-to-treat analysis, it is not sensitive to the number of individuals who drop out of the study after randomization. For secondary outcomes, based on pilot data and other relevant studies, we anticipate dropout from intervention in M-ROCC between 17-28% at 24-weeks and dropout in the control groups of 21-44% at 24-weeks.

In previous primary care studies, we have reported the impact of MTPC over 24 weeks on reductions in anxiety as measured by the PROMIS-ASF as  $d = -0.72$  ( $n=81$ ),  $p<0.001$  and  $d = -0.80$ ,  $p<0.001$  ( $n=136$ ). In our recent R21 pilot study, we reported significant Anxiety reductions over 24 weeks among patients with co-morbid anxiety at baseline ( $\geq 55$  at baseline) ( $p < .05$ ,  $ES = -0.556$ ). Given the

likelihood of a small effect of control on Anxiety after 4 weeks of buprenorphine treatment, we anticipate an effect size of  $d = -0.56$  for between-group change in PROMIS-ASF.

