We will compare intervention retention at 24-weeks, which is defined as having an active BUP prescription in the past 28 days at the 24-week study visit. In the chance case of imbalance of assignment, we will add the following variables as measurable covariates in regression models since they are known to impact retention: psychiatric diagnosis, age, gender, race/ethnicity, unemployment, previous opioid treatment, Hepatitis C, childhood trauma, baseline cocaine use, and injection drug use history. We will also add any other baseline characteristics that may be significantly imbalanced after randomization. We will also include key data collected during the first 4 weeks of the intervention, i.e., BUP non-adherence, self-reported illicit opioid use.

We will also measure time to intervention discontinuation, and fit Cox proportional hazard models that model the risk of time to intervention discontinuation, comparing hazard rates across the intervention and control groups, adjusting for the covariates described above in the logistic regression. All individuals that do not discontinue the

intervention at the end of data collection will be considered to be right-censored. We will assess the Cox proportional hazards assumptions using tests of Schoenfeld residuals and by visual estimation of log-log plots of the estimated survival curves. We will also use Wald tests to test significance in intervention vs. control group hazard rate differences.

We will also conduct a minimum of 12 qualitative interviews for M-ROCC or control group completers to examine themes regarding online mindfulness delivery and to compare responses with our R21 qualitative outcomes from our in-person group model.

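### The primary GEE does not commit to adjusting for baseline illicit opioid status, which is measured before randomisation; naming it as a fixed covariate would gain precision at no extra data collection

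*Combined protocol and SAP*

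**What the plan says.** **Primary model.** Section 9.6 (Primary Outcome) specifies a GEE over the six biweekly periods, "which accounts for the clustering of individual observations over time, with covariates". For dichotomous outcomes, "we will specify a binomial distribution and a logit link function, and robust standard errors clustered at the individual-level". No covariate is named there, and the modelled periods all lie in weeks 13-24, so baseline does not enter as an outcome either. By contrast, the secondary anxiety analysis in 9.6 is a change from baseline.

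**Covariates named elsewhere.**
- Section 4.3 makes scheduling acceptability a covariate in the statistical analyses generally.
- The retention paragraph of 9.6 (Exploratory analyses) says: "In the chance case of imbalance of assignment, we will add the following variables as measurable covariates in regression models". Its list includes baseline cocaine use, injection history and previous opioid treatment, but no baseline opioid test or recent illicit opioid use.
- The same paragraph adds any other baseline variable found significantly imbalanced. It also adds self-reported illicit opioid use from the first four weeks of the intervention.

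**What is measured before randomisation.** At the screening visit, "The RC will also supervise an oral fluid test with the participant to assess for substance use". Table 1a marks oral fluid toxicology at baseline. The PhenX core tool (Section 10.1) covers past-30-day use of the major substances.

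**Eligibility and allocation.** Criterion 5 in Section 4.1 has two routes. One begins "Less than 90 days of abstinence (from non-prescribed opioids or benzodiazepines, cocaine, or alcohol". The other is a co-morbid anxiety or stress disorder with no limit on length of abstinence. Section 6.2.2 uses blocks of 4, 6 or 8 and states no stratification factor.

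**The concern.** Eligibility can bring in both recent users and people with long abstinence. Opioid status at entry is therefore a plausible predictor of abstinent periods three to six months later. If it is prognostic and left out of the model, between-person variation that was known at baseline stays in the error of the primary test. Nothing in the allocation balances it by design.

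The plan leaves open whether it will be in the model. An unnamed covariate set allows several primary analyses. The nearest guidance in 9.6 points to two poor sources: variables picked because they differ significantly between arms, and opioid use measured after the intervention has begun. Conditioning on the second could absorb part of the effect being tested. Table 2 (Section 6.2.3) shows the data analysts and methodologists as not blinded, which makes open-ended covariate selection harder to defend.

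**Working it through.** **Inputs (Section 9.2).** Means 4.67 (SD 1.23) and 4.11 (SD 1.27) out of 6; 192 randomised; effective n 156, or 78 per arm. On the method: "This power calculation was generated assuming a t-test of the difference between two means, a 1:1 intervention to control recruitment ratio", with "a type I error of 0.05, a two-sided comparison, and a design effect of 1.23 derived from an ICC of 0.01" and "8 group clusters with average cluster size of 24".

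**Step 1: reproduce the plan's power.**
- Pooled SD = √((1.23² + 1.27²)/2) = 1.25, so d = 0.56/1.25 = 0.448, stated as 0.45.
- Design effect = 1 + (24 − 1) × 0.01 = 1.23, and 192/1.23 = 156.1.
- Power = Φ(0.45/√(2/78) − 1.96) = Φ(2.810 − 1.960) = 80.2%. The noncentral t gives 79.7%.

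The stated figure of more than 80% is reproduced, without spare margin.

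**Step 2: add a baseline covariate (linear approximation).** Let r be the correlation of baseline status with the 0-6 count. The residual SD falls by the factor s = √(1 − r²), and power = Φ(0.45/(s√(2/78)) − 1.96). The documents give no r, so it is an assumption.

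| Assumed r | s | Power, 78 per arm | Effective n per arm for 80% |
|---|---|---|---|
| 0 | 1 | 80.2% | 78 |
| 0.2 | 0.980 | 81.8% | 75 |
| 0.3 | 0.954 | 83.8% | 71 |
| 0.4 | 0.917 | 86.6% | 66 |
| 0.5 | 0.866 | 90.1% | 59 |

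**Step 3: check on the logit scale.** Six binary periods per person were simulated with 78 per arm and 1,500 replicates, using a logistic model with person-level robust standard errors. Two scenarios came closest to the planned SD (control-arm SD 1.34 and 1.37; r about 0.37 and 0.41). Adding a binary baseline covariate raised power from 76.3% to 82.8% and from 76.7% to 85.1%. These gains of 6 to 8 points agree with step 2. Scenarios with a larger SD started lower and gained between about 4 and 43 points, depending on r.

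**Step 4: does adjusting only on significant imbalance do the same job?** With 96 per arm, a standardised baseline difference just short of p = 0.05 is 1.96 × √(2/96) = 0.28 SD. It moves the unadjusted estimate by r × 0.28:
- r = 0.2: 0.06 SD, or 13% of the planned 0.45.
- r = 0.3: 0.08 SD, or 19%.
- r = 0.5: 0.14 SD, or 31%.

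No adjustment would be triggered. Over repeated trials this is variance, not bias, but fixed adjustment removes it and the trigger rule does not.

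**The case against.** A reader might infer that the plan has decided not to adjust. It has not: the GEE is run with covariates, and baseline opioid status is neither included nor excluded. The retention paragraph is not the plan's only covariate statement either, since scheduling acceptability is named in Section 4.3. The catch-all for imbalanced variables could also bring baseline opioid status in, although its place among the retention analyses leaves its reach to the primary model unclear. All of this stands. What remains is a missing commitment.

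A reader might also infer that the planned test is invalid or the power figure wrong. Neither follows. The randomised unadjusted comparison is valid, its variance already includes chance imbalance, and the power was calculated unadjusted and reproduces.

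It is tempting to call baseline opioid status the strongest predictor, or to treat the 90-day entry route as a stand-in for it. No document reports any baseline-outcome association. The 90-day route can be met through benzodiazepines, cocaine or alcohol alone, so it does not separate recent opioid users from others. Everyone must also have had at least four weeks on a stable buprenorphine dose, which may narrow the spread.

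Finally, the gain may be small: at r = 0.2 it is under two points. That limits the benefit but is no reason against adjustment, because the variables are already collected.

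**Conclusion.** The point holds as a missing commitment in the primary analysis: Section 9.6 does not guarantee adjustment for a baseline measure of the outcome that the trial already collects. It is a precision gain forgone, not an error in a stated figure.

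The size rests on an assumed correlation. From about 80% unadjusted, power would be about 82% to 90% for r from 0.2 to 0.5. This takes the plan's d, design effect and lack of an attrition allowance as given. It uses a linear approximation to a logit model, and the planning means count negative tests, whereas the primary outcome also requires no self-reported use. The change is worth making because the planned power has no margin and because it closes an open choice in the primary model.

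**What to change.** In Section 9.6 (Primary Outcome):

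1. Name the baseline oral fluid opioid result (same four-drug definition as the outcome) and past-30-day illicit opioid use from PhenX as fixed covariates, whatever the observed imbalance. State which pre-randomisation test counts if one is taken at both screening and baseline. Confirm that the PhenX items separate illicit opioids from prescribed buprenorphine.
2. List every other covariate in advance, including whether scheduling acceptability is one. Exclude weeks 1-4 data and any covariate chosen by a significance test of imbalance from the primary model. Include the fixed covariates in the imputation model.
3. With a logit link, the adjusted odds ratio is conditional on the covariates. Report as the effect the standardised (marginal) difference in mean number of abstinent periods: six times the difference in average predicted probability between arms. H1a refers to the number of periods but names no summary measure, so this should be written down. The plan already uses predictive margins for the secondary outcomes.
4. Adjust the cocaine and benzodiazepine outcomes for the matching baseline test in the same way.
5. Do not require an under/over-90-days indicator, because that criterion mixes substances.

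The cost is SAP wording, best fixed before any outcome data are compared by arm. No new data or participants are needed. Section 9.3 limits the intent-to-treat population to people who completed all baseline assessments, so these covariates should be essentially complete.

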### **Secondary Outcomes:**

A main **secondary outcome** is change in PROMIS-ASF at 24 weeks. To evaluate Anxiety as a secondary outcome, we will conduct a difference-in-differences, Intent-To-Treat, repeated measures analysis using linear mixed effects models (mixed) to evaluate time  $\times$  intervention assignment interaction from baseline to 24 weeks, using a selected sample of participants with a baseline PROMIS-ASF  $> 16$  (T-score  $> 55$ ), which is the cutoff for mild anxiety disorder (since PROMIS-ASF is non-linear below this score). An additional **secondary outcome** is change in PROMIS-Pain Interference (PROMIS-PISF) at 24 weeks. Mixed effects models account for clustering of multiple observations within participants. We will compute contrasts of predictive margins to test for significant within-group changes and difference-in-differences (between-group) estimates over time. Between-group and within-group effect size (Cohen's  $d$ ) will be computed based on the predictive margins generated from the mixed models. To address missing data, we will implement multiple imputation methods in Stata (mi procedure). This technique creates multiple complete datasets, imputes missing values using a probabilistic simulation method (e.g., chained equations), analyzes each dataset, and uses standard rules to combine estimates and adjust standard errors for the uncertainty of imputation. Other **secondary clinical outcomes** include the number of positive oral fluid tests for BZD or cocaine during the final 12 weeks of the study.

For secondary and exploratory outcomes, we will use the Benjamini-Hochberg false discovery rate (FDR) procedure, which accounts for multiple comparisons. We will implement FDR according to Cao et al. in which a cutoff  $p$  value is determined for a family of similar variables and analyses (family-wise error rate = 0.05). Statistical significance will be determined for the following analysis families: between-group main secondary clinical outcomes (family size,  $n = 4$ ), and exploratory self-regulation outcomes ( $n=8$ ), exploratory other mechanistic outcomes ( $n=4$ ), exploratory clinical/health outcomes ( $n=15$ ), formal practices ( $n= 4$ ), informal practices ( $n = 7$ ), and resource use ( $n= 7$ ) (see section 9.5.2 for details).

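### The sample size allows for correlation within treatment groups, but the primary GEE and the secondary mixed models treat members of the same therapy group as independent

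*Combined protocol and SAP*

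**What the plan says.** Section 9.2 (Justification of Sample Size and Power Calculations) uses "a design effect of 1.23 derived from an ICC of 0.01 with 8 group clusters with average cluster size of 24". It explains that 24 is the average number randomised in a monthly cohort to either arm, and that this level was chosen to cover cohort effects. The calculation is a t-test of two means with "a type I error of 0.05, a two-sided comparison".

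Section 9.6 (Primary Outcome) analyses abstinence over six biweekly periods by GEE. The model accounts for repeated observations on a person. For dichotomous outcomes it uses a binomial distribution, a logit link and "robust standard errors clustered at the individual-level". For the secondary outcomes, Section 9.6 says: "Mixed effects models account for clustering of multiple observations within participants". No therapy-group or cohort term is named in either model. The scheduling-acceptability covariate in Section 4.3 does not supply one.

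Both arms are delivered in separate live-online groups, with a new group in each arm every 4 to 5 weeks (Section 5.1).

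**The concern.** The plan pays for group correlation in its size and then omits it from its test. A sandwich variance protects against a wrong working correlation inside the declared cluster, but it assumes that different clusters are independent. Here the cluster is the person. Correlation between people in the same group stays outside the variance whichever working structure QIC selects.

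Such correlation is plausible on the protocol's own account. Section 5.1 sets a minimum group size because members influence one another. Section 6.2.6 expects the control groups to work through mutual support and role models. Section 9.6 collects group cohesion and attitudes to the leader as possible covariates or mediators. These influences belong to one group in one arm, so randomisation within a cohort does not cancel them.

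At stake is the error rate of the single confirmatory test, stated as 0.05, and the width of the primary and secondary intervals.

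**Working it through.** **Inputs.** From Section 9.2: 192 randomised (96 per arm), ICC 0.01, 8 clusters of 24, d = 0.45 (means 4.67 and 4.11, SDs 1.23 and 1.27), two-sided 0.05. Since 8 × 24 = 192, each cluster of 24 is a whole cohort with both arms in it, so an arm-specific group holds about 24/2 = 12 people and there are about 16 such groups.

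**1. The plan's own figures.**
- Design effect: 1 + (24 − 1) × 0.01 = 1.23.
- Effective N: 192/1.23 = 156.1, or 78 per arm.
- Power: Φ(0.45 × √(78/2) − 1.96) = Φ(0.850) = 80.2%. An exact t calculation gives 79.7%.
- With no design effect: Φ(0.45 × √(96/2) − 1.96) = 87.7%.

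The stated figures reproduce, and the allowance for clustering is a real one.

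**2. What the individual-level test leaves out.** Let s be the share of variance common to both arms of a cohort, g the share specific to a group of m people, and 1 − s − g the individual share. The shared part cancels from the arm contrast. The true variance of the contrast, relative to what the individual-level test assumes, is approximately

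R = m·g + (1 − s − g) = 1 + (m − 1)g − s,

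and the actual error of the nominal 5% test is 2 × [1 − Φ(1.96/√R)].

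| Where the correlation lies (m = 12) | R | Error, formula | Error, simulated |
|---|---|---|---|
| All 0.01 arm-specific | 1 + 11 × 0.01 = 1.11 | 6.3% | 6.4% |
| Half shared, half arm-specific | 1 + 11 × 0.005 − 0.005 = 1.05 | 5.6% | 5.4% |
| All 0.01 shared by both arms | 1 − 0.01 = 0.99 | 4.9% | 4.9% |
| Assumed arm-specific ICC 0.02 | 1 + 11 × 0.02 = 1.22 | 7.6% | 7.5% |
| Assumed arm-specific ICC 0.05 | 1 + 11 × 0.05 = 1.55 | 11.5% | 11.4% |

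The simulations used 8 cohorts, 2 arms and 12 people per group, with 40,000 runs. A further check of the even split widens its range to about 5.4 to 5.8%. With R = 1.11 the standard error is too small by 1 − 1/√1.11 = 5%.

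Section 5.1 gives 6 to 15 people for an intensive group. With the whole 0.01 arm-specific, that range gives R from 1.05 to 1.14 and an error from 5.6% to 6.6%.

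A binary version (six periods per person, logit contrast, sandwich on the individual) behaves in the same way. It gave 5.5% with no group correlation, 7.2% when the arm-specific ICC of the counts was about 0.015, and 5.0% when a similar correlation was shared by both arms.

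**3. Power with the group as the cluster.**
- Design effect 1.11; effective N 192/1.11 = 173, or 86.5 per arm.
- Noncentrality: 0.45 × √(86.5/2) = 2.96.
- Reference: t with 16 − 2 = 14 df, critical value 2.145.
- Power: 78.6% for d = 0.45, and 78.2% for d = 0.448 from the stated means and SDs. The normal approximation gives 84.1%, so the shortfall comes from the degrees of freedom.
- Interval width relative to the planned analysis: √1.11 × 2.145/1.96 = 1.054 × 1.094 = 1.15.

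**The case against.** The strongest reply is that the ICC of 0.01 is attached to a cohort containing both arms. If it describes an effect common to both arms, it cancels, and the planned test keeps its level (4.9%). The documents give no ICC for arm-specific groups. This stands, and it makes the inflation conditional. It does not remove the gap, because the arms meet separately and the plan treats group process as active.

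A reader might carry the 1.23 straight into the test and infer an error of 7.7% (1.96/√1.23 = 1.767). The documents do not support that: the 1.23 rests on the mixed-arm cohort of 24, which is not the unit that inflates the arm contrast.

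A reader might also infer that Section 9.2 under-allows for clustering. On variance the reverse is true, since 156 is smaller than 173. Only the small number of groups takes power below 80%.

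A further objection is that fixed groups of 12 are not what exists in weeks 13 to 24. By then M-ROCC participants may have repeated LDM, joined an MTPC-OUD group or moved to MCS (Précis and Section 5.1), and about half are expected to start MTPC-OUD. This also stands. First-assigned group may miss correlation that arises later, so the plan needs a rule for movers and a sensitivity analysis.

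Finally, the sentence on standard errors is worded for dichotomous outcomes, while Section 9.5.1 defines a count from 0 to 6. It fits the biweekly GEE, and no other standard-error rule is given for the count. For the secondary outcomes no inflation was computed. The anxiety analysis uses only participants above the baseline cutoff, so its groups, and its design effect at a given ICC, are smaller.

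**Conclusion.** The mismatch between Sections 9.2 and 9.6 is real and should be corrected before the analysis. Its direction holds for any positive arm-specific correlation large enough to outweigh the shared part. Its size at the plan's own ICC is modest: about 6.3% if all of the 0.01 is arm-specific, about 5.4 to 5.8% for an even split, and no inflation if it is all shared. These figures assume about 16 fixed groups of about 12.

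The documents do not support an unconditional statement that the primary test exceeds 5%. Values such as 11.5% rest on an ICC of 0.05 that appears nowhere in the plan. They show sensitivity and are not an estimate.

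**What to change.** **Section 9.6, primary.** Name the group first assigned (cohort by arm, about 16) as the cluster. Use a sandwich variance with a small-sample correction (Fay-Graubard or Mancl-DeRouen) and a t reference, or a mixed logistic model with random intercepts for assigned group and participant. Adjust for cohort and state how. Eight fixed cohort effects would leave about 16 − 8 − 1 = 7 df for a group-level comparison instead of 14, so the choice should be made in advance.

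**Section 9.6, secondary.** Add the same group random intercept and cohort adjustment to the mixed models.

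**Movers.** State that participants who later repeat LDM or enter MTPC-OUD or MCS are analysed in the group first assigned. Add a sensitivity analysis by the group actually attended during weeks 13 to 24.

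**Section 9.2.** Restate the design effect at therapy-group level (about 1.11, effective N about 173), with power on about 14 df of about 78 to 79%. Mark the arm-specific ICC as an assumption and show a range.

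**Cost.** SAP wording and some code. Start week and arm are set at randomisation, and attendance already goes to REDCap (Section 5.1), so no new participants or measurements are needed. Intervals become about 15% wider, mainly because there are few groups, and the claim of more than 80% power has to be lowered.
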